## I. BACKGROUND AND SIGNIFICANCE

Sevoflurane is an anesthetic agent with a rapid induction, emergence and recovery profile. Evidence suggests that sevoflurane, similar to other ether derivatives in clinical use, exerts its physiological and behavioral effects by binding at multiple targets in the brain and spinal cord. Action at these targets includes potentiation of  $\gamma$ -Aminobutyric acid (GABAA), glycine and two-pore potassium channels; and inhibition of voltage-gated potassium, N-methyl-D-aspartate (NMDA), muscarinic and nicotinic acetylcholine (ACH), serotonin, and  $\alpha$ -Amino-3-hydroxy-5-methyl-4-isoxazolepropionic acid (AMPA) channels. Despite detailed characterizations of the molecular and cellular pharmacology of anesthetics, the neural circuit-level mechanisms of general anesthesia-induced unconsciousness are still being actively investigated. Extensive work has related in detail the electroencephalogram (EEG) patterns of propofol (2,6-diisopropylphenol) to its neural circuit mechanisms. Propofol primarily acts at GABAA receptors throughout the brain and spinal cord to enhance inhibition. It also potentiates glycine receptors, and provides inhibition to voltage-gated potassium, ACH, AMPA and Kainate channels. Given the diversity of receptor targets, a unitary hypothesis of the neural circuit mechanism underlying anesthesia-induced depression of consciousness does not seem likely. However, clinically, we have observed that sevoflurane induces stereotypical changes in the EEG that appear grossly similar to propofol and that may help relate this anesthetic vapor to its neural circuit mechanisms.

Our previous work provides compelling evidence that unconsciousness under propofol is characterized on the EEG by alpha (8-12 Hz) oscillations that are coherent across the frontal cortex, delta (1-4 Hz) oscillations and high amplitude slow (0.1-1Hz) oscillations. Intracortical recordings during propofol-induced unconsciousness suggest that local and long-range cortical communication are impeded by temporally and spatially incoherent slow oscillations that exhibit phase-limited spiking. Analysis of the scalp EEG, a readily accessible measure of the average activity in large populations of cortical neurons, has established that propofol induces synchronous frontal alpha oscillations. Biophysical modeling provides further evidence that propofol induces coherent alpha activity by increasing GABAA conductance and decay time. This increase in GABAA conductance facilitates involvement of the thalamus in a highly coherent thalamocortical alpha oscillation loop. This pathologically coherent frontal alpha oscillation pattern reduces the dimensionality of the thalamocortical network, reducing the ability of the thalamus to project and coordinate exogenous inputs to the neocortex.

Coherent alpha oscillations have also been identified in animal studies of the inhaled anesthetics during unconsciousness. However, human studies examining this cortical dynamic are non-existent. Given that both sevoflurane and propofol are known to act at GABAA receptors, studying the EEG patterns elicited by sevoflurane using the novel paradigms we have previously established to study propofol will provide insights on the neural circuit mechanisms of sevoflurane. Previous studies employing EEG-based methods, including spectral analysis, bispectral analysis, auditory evoked potentials and methods for source localization, have been used to compare the conscious and unconscious states under general anesthesia, usually from surgical recordings taken before and after a rapid induction of general anesthesia. However, none of these methods have been used to track, on a moment-to-moment basis, the

transition to unconsciousness during a gradual induction of general anesthesia with an anesthetic vapor, nor the return of consciousness.

We have recently studied the similarities and differences in EEG spectra and coherences between sevoflurane and propofol in data recorded during routine care of patients in the intraoperative setting [publication in review]. We found the following: (i) Similar to propofol-induced frontal alpha oscillations, sevoflurane is characterized by coherent alpha oscillations with similar maximum power and coherence occurring at ~10-12 Hz; (ii) Also similar to propofol, sevoflurane is associated with slow oscillations characterized by similar power and coherence at frequencies < 1 Hz; (iii) In contrast to propofol, sevoflurane is associated with increased power in the theta band. These theta oscillations are coherent across the frontal cortex and may provide additional insight into the neural circuit mechanisms of sevoflurane especially with regards to thalamic dysrhythmia and deafferentation. However, since the EEG recordings we analyzed were obtained solely from frontal channels in a clinical setting, we were unable to perform detailed characterizations of changing behavior and consciousness during controlled induction and emergence, limiting our inferences to a clinically unconscious state. Also, the nature of data (frontal channel only) limited our ability to analyze the cortical dynamics underlying sevoflurane anesthesia-induced unconsciousness.

Therefore, we propose a paradigm to use EEG measurements to study the dynamics of loss of the changes to well-designed sensory or cognitive “probes.” This study will help address the compelling need to replace the current clinical definitions of general anesthesia with neurophysiological and neuroanatomical definitions of the state of general anesthesia. By using principled auditory, and somatosensory asks, results from this study will help establish the relation between EEG changes and loss of consciousness. This may provide insights into the neural circuit mechanisms through which sevoflurane and other ether derivatives induce unconsciousness. The detailed characterization and comprehension of these mechanisms may prove vital for shaping future studies on establishing the neural correlates of consciousness.

## II. SPECIFIC AIMS

The specific aims of this study are:

**AIM 1:** To use high-density EEG recordings to characterize the different brain-states induced by the anesthetic vapor, sevoflurane.

**Hypothesis 1a.** The onset and stable maintenance of sevoflurane-induced beta oscillations will signify a sedative brain state with a probability of response to auditory and nociceptive stimuli that approaches the awake state.

**Hypothesis 1b.** The onset and stable maintenance of highly coherent sevoflurane-induced frontal alpha and theta oscillations will signify a brain-state approaching a zero probability of response to auditory and nociceptive stimuli.

**Hypothesis 1c.** Sevoflurane-induced large slow oscillations (at maximum amplitude) and burst suppression will signify a brain state with a zero probability of response to auditory stimuli.

**Hypothesis 1d.** Return of consciousness will be preceded by return of gamma oscillations and the loss of large amplitude slow, theta, alpha and beta oscillations.

**AIM 2:** To use high-density EEG recordings to understand the neural-circuit mechanism of action of ether anesthetics.

**Hypothesis 2a.** The administration of an N-methyl-D-aspartate receptor antagonist (ketamine) during sevoflurane-induced unconsciousness (putative  $\gamma$ -aminobutyric acid mechanism) will antagonize and significantly diminish the amplitude of the alpha and slow oscillations.

**Hypothesis 2b.** The administration of an N-methyl-D-aspartate receptor antagonist (ketamine) during sevoflurane-induced unconsciousness (putative  $\gamma$ -aminobutyric acid mechanism) will produce globally non-coherent beta oscillations that are sufficient to maintain a brain state with a zero probability of response to auditory stimuli.

**Hypothesis 2c.** The administration of an N-methyl-D-aspartate receptor antagonist (ketamine) during sevoflurane-induced unconsciousness (putative  $\gamma$ -aminobutyric acid mechanism) will antagonize the effects of sevoflurane on airway collapsibility by mediated by  $\gamma$ -aminobutyric acid inhibition on the hypoglossal motor neuron.

**AIM 3:** To use inflammatory profiling of serum to understand the effect of sevoflurane on systemic inflammation

**Hypothesis 3a:** We hypothesize that sevoflurane-anesthesia will be associated with increased levels of pro-inflammatory cytokines interleukin 6 and TNF-alpha.

**Hypothesis 3b:** We hypothesize that sevoflurane/ketamine-anesthesia will be associated with decreased levels of pro-inflammatory cytokines interleukin 6 and TNF-alpha.

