Behavioral Analysis: The probability of response to the click and verbal stimuli and the difference in probability of response will be estimated by using Bayesian Monte Carlo methods to fit a state-space model to these data. To perform group-level analyses, we will align the behavioral data across subjects with respect to each subject's LOC time for induction and with respect to each subject's ROC time for emergence. We will then pool the responses within bins. The pooled data will be used to estimate group-level probabilities of response using the state-space model.

Spectral Analysis: We will compute spectrograms for all subjects using the multitaper method. We will also compute group-level baseline-normalized spectrograms for induction and emergence by taking the median across subjects with the data aligned to the LOC and ROC time points, respectively. To determine if the group-level spectrogram is significantly greater than baseline, we will perform a two-group-test as implemented in chronux.

Eigenvalue and Modal Projection Analyses: We will perform an eigenvector decomposition analysis of the cross-spectral matrix to identify the principal modes of oscillation in the conscious and unconscious states and to analyze how activity within these principal modes change through time. We will estimate the cross-spectral matrices  $P_{\text{baseline}}(f)$  and  $P_{\text{unconscious}}(f)$  at each frequency  $f$  using the multitaper method using data from the full baseline period, and segments of at least 5 min extending from LOC to ROC, respectively, for each subject. An eigenvalue decomposition of the median cross-spectral matrix at each frequency will be performed. Each eigenvector describes a

coherent spatial distribution or mode of oscillation, and the corresponding eigenvalue quantifies the power in this mode. We then use modal projection analysis to characterize how power within principal modes change as a function of time. A permutation-based procedure will be performed to assess statistical significance for the modal projection analysis.

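### Hypotheses 1b and 2b each contain a coherence claim, but the planned EEG analyses specify only power measures across channels, so the coherent/non-coherent part of either hypothesis cannot be confirmed as the plan stands

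*Combined protocol and SAP*

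**What the plan says.** Section II (Specific Aims) words two EEG hypotheses in terms of coherence. Hypothesis 1b states that "highly coherent sevoflurane-induced frontal alpha and theta oscillations will signify a brain-state approaching a zero probability of response" to auditory and nociceptive stimuli. Hypothesis 2b states that ketamine given during sevoflurane-induced unconsciousness "will produce globally non-coherent beta oscillations that are sufficient to maintain a brain state" with zero probability of response to auditory stimuli.

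Section VI (Biostatistical Analysis) has one cross-channel method, under Eigenvalue and Modal Projection Analyses: "We will perform an eigenvector decomposition analysis of the cross-spectral matrix to identify the principal modes of oscillation". It describes each eigenvector as a coherent spatial pattern and adds that "the corresponding eigenvalue quantifies the power in this mode". The time course is also in power: "We then use modal projection analysis to characterize how power within principal modes change as a function of time". The test is attached to that quantity: "A permutation-based procedure will be performed to assess statistical significance for the modal projection analysis". The states compared are baseline and the period from loss to return of consciousness.

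The section also plans multitaper spectrograms tested against baseline, a phase-amplitude histogram, and a state-space model for the probability of response. It defines no coherence statistic and no cut-off for high coherence or its absence.

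**The concern.** Power and coherence are different properties. Every cross-spectral matrix has eigenvectors, including that of statistically independent channels, so calling an eigenvector coherent does not measure how coherent the channels are. An unnormalised eigenvalue grows when all channels gain power at constant coherence, and it also grows when only incoherent power is added.

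The distinction matters to this plan's own argument. Section I builds its account of unconsciousness on coherent frontal alpha and reports power and coherence as separate findings in the group's intraoperative data. If coherence is left to be chosen at analysis, the measure, electrodes, band and cut-off would be picked after the data are seen. Mode power might also be offered as evidence for a property that it does not isolate. Hypothesis 2b has a further gap: the eigen-analysis states no comparison with and without ketamine.

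**Working it through.** **The plan's own figures.** The plan gives no number for coherence. Its only design calculation is for Global Precedence: (3 × (1.645 + 1.282) / 3)² = 8.56, rounded up to 9. This reproduces the stated 9 but has no bearing on the present point.

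**Step 1: what each planned EEG quantity measures.**
- Spectrograms: power, tested against baseline.
- Eigenvalues: power in a mode, not divided by total power.
- Modal projection: power in a mode over time, with a permutation test.
- Phase-amplitude histogram: slow phase against 8–14 Hz amplitude, not described as cross-channel.

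None is a degree of coherence between channels.

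**Step 2: one shared source.** The documents give none of the inputs, so these are assumed: K = 64 channels, each with coherent power a = 0.3 and incoherent power b = 0.7. The cross-spectral matrix is a·11ᵀ + b·I. Its leading eigenvalue is λ₁ = Ka + b, and its eigenvalues sum to K(a + b).

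| Scenario | λ₁ | Sum | λ₁/sum |
|---|---|---|---|
| Reference | 64×0.3 + 0.7 = 19.9 | 64.0 | 0.31 |
| All power ×4 | 64×1.2 + 2.8 = 79.6 | 256.0 | 0.31 |
| Coherent part only ×4 | 64×1.2 + 0.7 = 77.5 | 121.6 | 0.64 |
| Incoherent part only ×10 | 64×0.3 + 7.0 = 26.2 | 467.2 | 0.06 |

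Rows two and three have nearly the same λ₁ but different coherence. In row four λ₁ rises while coherence falls. A simulation with 450 independent spectral estimates per matrix (also assumed) gave 20.0, 79.7, 77.4 and 27.3 for the four rows.

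**Step 3: a second model.** Let every channel have power s and every pair coherency r, so that λ₁ = s(1 + (K − 1)r). With K = 64:
- Base (s = 1, r = 0.3): λ₁ = 1 + 63×0.3 = 19.9; share 19.9/64 = 0.311.
- Coherence only (s = 1, r = 0.9): λ₁ = 1 + 63×0.9 = 57.7; share 57.7/64 = 0.902.
- Power only (s = 57.7/19.9 = 2.90, r = 0.3): λ₁ = 57.7; share 0.311.
- Power ×4 with r = (19.9/4 − 1)/63 = 0.063: λ₁ = 19.9, unchanged from base; share 19.9/256 = 0.078.

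The power ratio that mimics a move in r from 0.3 to 0.9 depends on K: 3.7/1.9 = 1.95 for 4 channels, 2.90 for 64, and 230.5/77.5 = 2.97 for 256.

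**Step 4: does the simple ratio cure it?** Not fully. Take 64 independent channels, with 10 of them at 20 times the power of the rest. Coherence is zero, yet λ₁/sum moves from 1/64 = 0.016 to 20/(54 + 200) = 0.079. If each channel is first scaled to unit power, the ratio is 1/64 in both cases. The shares in steps 2 and 3 do not change under that scaling, because all channels there have equal power.

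**The case against.** A reader might infer that neither hypothesis can be confirmed or refuted at all. The documents do not support that. Both hypotheses also predict that certain oscillations appear, which the spectrograms address, and that response probability to auditory stimuli is near zero or zero, which the state-space model estimates. Failure of either prediction would count against the hypothesis.

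A reader might also infer that these data cannot separate a coherence change from a power change. That is true only of the leading eigenvalue read alone. The decomposition yields all eigenvalues, and spectrograms are planned for every subject. In the step 2 scenarios total power rises 4.0-fold, 1.9-fold (121.6/64) and 7.3-fold (467.2/64) from reference. Set beside λ₁, that tells the cases apart. The gap is in the prespecification, not in the data or design.

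Nor does 2b need coherence in order to be told apart from 1a, which ties beta to a responsive state. Drug condition and the opposite predicted response probabilities already separate them.

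Three further objections carry weight. The numerical inputs are assumed, and the tenfold incoherent rise was chosen to show the direction of the problem. No passage says how 1b will be judged, so it is conjecture that a rise in alpha power would be reported as support. And 1b and 2b are mechanistic hypotheses with no allotted type I error; the only sized endpoint is Global Precedence.

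What remains is that the plan does choose a cross-channel statistic and a test, and neither measures the property named in the hypotheses.

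**Conclusion.** The point holds in limited form. Section VI specifies no coherence measure, contrast, threshold or test for 1b or 2b, and its cross-channel outputs are power. The coherent/non-coherent component therefore cannot be confirmed by the stated analyses, and without it neither hypothesis can be confirmed as worded. Other components of both remain open to refutation.

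The algebra that λ₁ mixes power with coherence is general. The sizes shown (79.6 against 77.5, or 57.7 in both cases) are illustrative and depend on the assumed channel number, coherent fraction and scaling factors. They are not estimates for this trial. The plan should be changed on this point, but the point does not touch the sample-size endpoint or call the study design into question.

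**What to change.** Add a short paragraph to Section VI, under Eigenvalue and Modal Projection Analyses:
- **Measure.** For each subject and epoch, scale the multitaper cross-spectral matrix to unit power per channel (the coherency matrix). Take the largest eigenvalue divided by the sum of eigenvalues at each frequency. Use the same number of spectral estimates in every epoch compared, so that small-sample inflation of the ratio does not differ between conditions.
- **Hypothesis 1b.** Frontal electrodes, alpha and theta bands, baseline against the period from loss to return of consciousness.
- **Hypothesis 2b.** All electrodes, beta band, with a within-subject contrast of sevoflurane against sevoflurane/ketamine (or before against after ketamine).
- **Test.** Use the permutation approach already planned for both, and name the electrode sets, band limits and time windows in advance.
- **Existing outputs.** Keep the eigenvalue and modal-projection results, labelled as measures of power only.

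The cost is a few lines of text and one more summary per band, with no new data or procedures. The practical constraint is having enough tapers and segments relative to the number of channels, which may be as high as 256. That may require longer epochs or a reduced electrode set, fixed beforehand.

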### III. SUBJECT SELECTION

We will select 24 volunteer subjects (male and female) between the ages of 18-50 years. The subjects will be recruited using:

- An announcement of the study distributed through the Partners Public Affairs distribution list.

All study subjects will be American Society of Anesthesiologists (ASA) physical status classification P1. That is, all study subjects will be fit and healthy. A complete medical history will be taken and a complete physical examination will be given to rule out active and chronic medical problems.

#### Primary Inclusion Criteria for Subjects

- Between the ages of 18 and 50
- Normal body weight and habitus, BMI  $\leq$  30
- Non-smoker
- American Society of Anesthesiologists (ASA) physical status classification P1

#### Medical Reasons for Exclusion

Chronic health conditions that will exclude subjects from the study include but are not limited to:

Cardiovascular: hypertension, myocardial infarction, and coronary artery disease, peripheral vascular disease, arrhythmia, congestive heart failure, valvular disease

Respiratory: sleep apnea, bronchitis, chronic obstructive pulmonary disease, smoking, shortness of breath

Hepatic: hepatitis, jaundice, ascites

Neurologic: seizure, stroke, positive neurologic findings on neurologic examination, multiple sclerosis, Meniere's disease, Parkinson's disease

Gastrointestinal:	esophageal reflux, hiatal hernia, ulcer
Endocrine:	glucose intolerance, diabetes, thyroid disease
Renal:	acute or chronic severe renal insufficiency
Hematologic:	blood dyscrasias, anemia, coagulopathies, on anticoagulant therapy
Musculoskeletal:	prior surgery or trauma to head neck or face, arthritis, personal or family history of malignant hyperthermia
Psychiatric:	claustrophobia, history or treatment for an active psychiatric problem, depression
Reproductive:	pregnancy, breastfeeding
Medications:	regular use of prescription and non-prescription medications expected to affect CNS function
Allergies:	sevoflurane, phenylephrine, glycopyrrolate, ketamine, haldol

#### Remuneration

For successful completion of this protocol, subject remuneration will be \$800. If the study subject is unable to complete the entire protocol, pro-rating of this remuneration will be as follows:

- Study subjects who complete the medical screening evaluation but do not begin the anesthesia portion of the study will receive \$50.
- Study subjects who complete the medical screening evaluation, and one anesthesia study visit will receive \$250.
- Study subjects who complete all study portions will receive \$800.

Parking vouchers will be available on study days.

#### **IV. STUDY PROCEDURES**

##### Location:

The screening visit will take place at the White 12 Clinical Research Center.

The anesthesia portion of these studies will take place on White 5 at the Carl Rosow Center for Clinical Research. White 5 was constructed specifically for the performance of research on human subjects receiving the depressant medications used in anesthesia. The research area is built to the same standard as a typical surgical procedure room at MGH with respect to ventilation, temperature control, plumbing and electrical facilities, as well as storage for sterile supplies and linens. There is piped oxygen and air, wall suction and waste anesthetic gas removal. Electrical outlets are supported by the hospital's backup generator. There is a fully-equipped anesthesia machine with an automated record keeper and standard anesthesia monitors. A fully equipped code cart is immediately available, and an emergency call system is connected to the White 3 PACU. The code cart and medications are checked at intervals by personnel from the

OR pharmacy, and the anesthesia equipment is safety checked and maintained by Anesthesia Bioengineering. In short, research subjects receiving anesthetic drugs in this unit are given an identical standard of care as patients in our operating rooms. Any research protocol utilizing this space must first be reviewed by a DACCPM committee specifically created to ensure appropriate standards of anesthetic care and the safety of human subjects.

**Screening Visit:**

All subjects will complete a screening visit. Study subjects will arrive at the study site to undergo screening to ensure that they meet the basic inclusion/exclusion criteria for the study and give written informed consent. All questions will be explained as needed. All women of childbearing age will be tested for pregnancy. A urine hCG pregnancy test will be performed. If the test performed comes back negative for pregnancy, the subject will be enrolled. If the test performed comes back positive for pregnancy or the subject is breastfeeding, the subject will not be enrolled in the study. If the test performed comes back borderline, we perform another test.

Consent Procedures: Prior to the study, each subject will sign an informed consent form. The investigator obtaining consent will explain in detail the protocol of the study, its purpose and potential benefits to the society. Subjects will be informed that if they feel uncomfortable with the study, they can choose to terminate the study at any time.

Physical Examination: The subjects will be given a standard pre-anesthetic physical examination. Particular attention will be paid to the subject's airway anatomy and neurologic function. Any abnormal findings on physical examination will be reason for exclusion from the study. Abnormal findings will be reported to the subjects and recommendations for medical follow-up will be given as needed.

Screening Tests: A complete blood count, blood glucose level, liver function tests (LFTs), blood urea nitrogen (BUN), and creatinine (Cr) level will be obtained at the initial screening visit. For inclusion into the study protocol, each subject will be required to have a platelet count, blood glucose, BUN levels, Cr levels, white blood cell count, hemoglobin, differential and LFTs within 2 times the upper and lower limit of normal. Any subject who tests positive for any "street drugs" (amphetamine, barbiturates, benzodiazepines, cannabinoids, cocaine, opiates, or phencyclidine) may be excluded from the study. An ECG will also be performed.

Randomization: Visits 1 and 2 will be randomized to determine their order of occurrence: sevoflurane only vs. sevoflurane with ketamine.

